To address these practical limitations and fully leverage the potential therapeutic benefits of sensory stimulation, we have developed a new stimulation that is imperceptible random-frequency vibration applied to wrist skin via a watch. We determined the optimal stimulation parameters (location, intensity, and frequency) based on our experimental data^{12, 13} and literature.¹⁴⁻²⁵ The theoretical framework is that imperceptible random-frequency vibration stimulates mechanoreceptors in wrist skin and afferents,^{26,27} adds small random currents to neurons in the sensorimotor cortex, triggering coherent¹⁶ firing¹⁸ at the peak of inputs related to hand tasks, and consequently enhances neural communication^{15, 28} for hand tasks¹⁴ and functional recovery. Our pilot data support the theoretical framework by demonstrating that neuronal firing magnitude and coherence in the cortical sensorimotor network for hand tasks increased with vibration vs. without, as measured by electroencephalogram (EEG). In addition, preliminary efficacy has been demonstrated in two pilot studies. First, use of vibration during 2-wk task-practice therapy resulted in greater improvement in manual dexterity assessed by the Box and Block Test (BBT) than dose-matched therapy alone, which sustained at follow-up (19 days post intervention).²⁹ Second, use of vibration during 6-wk task-practice therapy resulted in greater mean improvement in movement time assessed by the Wolf Motor Function Test (WMFT) compared with 10-wk task-practice therapy³⁰ and 12-wk manual therapy³¹ alone both at post and follow-up evaluations.

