9.0 Study Design / Methods

Study design: The study design is a double-blinded randomized controlled study. Participants will undergo standardized hand task practice therapy (3 sessions/week for 6 weeks) with the watch worn on the paretic wrist. Participants will be randomized into two groups: The device will deliver vibration for the treatment group and no vibration for the control group during therapy. Half the participants will be in the treatment group, and half in the control group. Double blinding is possible since treatment vibration is imperceptible (i.e., subthreshold). Evaluation will be performed at baseline, after 2, 4, and 6 weeks of continuous task practices and at 1-month follow-up.

Schedule: Participation will last 2.5 months. Participants' involvement entails 18 visits for therapy (each lasting 1-2.5 hours, 3 sessions/week for 6 weeks) and 2 evaluation visits (evaluations at each time point divided into 2 visits to minimize fatigue) for each of the 3 time points (baseline, after therapy, and follow-up), along with one time only, 30-min MRI assessment, resulting in a total of 25 visits over 2.5 months. Each activity is described below.

Therapy: Participants will undergo a standardized hand task-practice therapy program. Upper limb tasks for activities of daily living that are of the participants' interests and are related to participants' goals will be chosen and practiced with repetitions, in the laboratory. The difficulty level of the tasks will be modified per participants' progress. To translate improved motor capacity to independence at home, the paretic hand use in daily tasks at home will be tracked and encouraged.

Evaluation: Each of the two evaluation visits will last approximately 2-5 hours. The following assessments will be performed across the two evaluation visits.

Upper limb function assessment: Clinical upper extremity function scores will be assessed using conventional clinical assessments used in occupational/physical therapy in which participants will be asked to move the affected hand and arm, grasp objects and perform prescribed tasks (e.g., lifting an object off the table, releasing the object into a bin) as quickly as possible or at a comfortable speed, upon cues. These tests

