10.0 Data Management

Recruitment: Recruitment projects are housed in REDCap. Only study personnel will have access to the REDCap database while actively enrolling for the study.

Analysis: The primary analysis will be a repeated measures ANOVA for each outcome. The dependent variables will be the change from baseline at the evaluation times. The primary independent variables are group, evaluation time, and their interaction. We will also include sex as a biological independent variable along with its interactions. If the group by time interaction is significant, we will examine if there is a group difference at 10 weeks using post-hoc tests.

Sample size justification: The clinically meaningful difference in time needed to complete a functional upper limb task is deemed to be 4 to 7 s. This study will be powered to detect difference at follow-up of at least 4s in movement time between the treatment and control groups. For the repeated measures design with a significance level of 0.017 (adjusted for multiple comparison), at least 80% power, and 4 time points, for a standard deviation (SD) of 5.1s and compound symmetry correlation of 0.92 (both based on our pilot study²⁹), sample size of 32/group will be adequate. Adjusting for 15% attrition, 38/group is planned (total n=76).

Confidentiality: All data except for the consent forms and HIPPA forms will be coded at the time of data recording. All electronic data will be stored in a password-protected research server that is accessible to study personnel only. Videos of the upper limb movement will be recorded such that we will avoid capturing the participant's face, while capturing the hand, arm, and object being gripped. All paper data with personally identifiable information including the consent forms and HIPPA forms will be stored in a key-locked cabinet in a key-locked room that is accessible to study personnel only. Other paper data without personally identifiable information including testing sheets documenting testing sequences and notes will also be stored in a cabinet in a key-locked room that is accessible to study personnel only.

Data sharing: Only de-identified coded data will be reported and/or shared with the public and other investigators

in publications, in ClinicalTrials.gov, or via data depository.

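### The model for change from baseline does not adjust for the baseline value, which gives up some precision in the group effect and the 10-week difference at almost no saving

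*Combined protocol and SAP*

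**What the plan says.** In Section 10.0 (Data Management), the Analysis paragraph specifies a repeated measures ANOVA for each outcome: "The dependent variables will be the change from baseline at the evaluation times". It then lists the terms: "The primary independent variables are group, evaluation time, and their interaction". The only addition is sex: "We will also include sex as a biological independent variable along with its interactions". The 10-week comparison is conditional: "If the group by time interaction is significant, we will examine if there is a group difference at 10 weeks using post-hoc tests".

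Baseline is measured. Section 9.0 states: "Evaluation will be performed at baseline, after 2, 4, and 6 weeks of continuous task practices and at 1-month follow-up". It enters the analysis only by being subtracted; no section adds it as a covariate.

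The sample size paragraph of Section 10.0 gives the target: "This study will be powered to detect difference at follow-up of at least 4s in movement time between the treatment and control groups". It uses a significance level of 0.017, at least 80% power and 4 time points, "for a standard deviation (SD) of 5.1s and compound symmetry correlation of 0.92". The result is 32 per group, raised to 38 for 15% attrition. It does not say whether the SD and correlation describe raw movement times or changes.

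**The concern.** Subtracting baseline fixes the slope of follow-up on baseline at 1. With equal SDs and correlation rho, the best slope is rho. The unadjusted contrast therefore carries -(1 - rho) times any chance baseline difference between groups, and its variance is larger than it need be unless rho is very close to 1. Randomization makes that residue average to zero, so the test stays valid. In the one trial that is run, the estimate is still shifted by it.

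What is at stake is the precision of the group effect and of the 10-week difference, the quantity for which the trial is to be powered. The same model is planned for every outcome, and the only correlation given is the one in the movement-time calculation. The covariate also has to be chosen in advance, because adding it after results are seen invites challenge.

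**Working it through.** **Inputs (Section 10.0):** difference 4 s; SD s = 5.1 s; rho = 0.92; alpha 0.017, taken as two-sided; power 80%; 4 time points; n = 32 per group. Section 9.0 has four post-baseline times. The calculations below leave out the sex terms.

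**1. The plan's sample size.** For a group difference averaged over 4 times under compound symmetry:

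- n = 2 s² × [(1 + 3 rho)/4] × (z.9915 + z.80)² / 4²
- (1 + 3 × 0.92)/4 = 0.94; z sum = 2.387 + 0.842 = 3.228
- n = 2 × 26.01 × 0.94 × 3.228² / 16 = 31.85, so 32 per group. This matches the plan, and 32/0.85 = 37.6, so 38.

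The formula has no baseline term. For a single time point it gives 33.9.

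**2. Variance at one time point, equal SDs.**

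- Change score: 2 s²(1 - rho)
- Baseline-adjusted: s²(1 - rho²)
- Ratio: (1 + rho)/2
- Net of estimating the slope: multiply by 1 + 1/(2n - 4) = 1 + 1/60

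| rho | ratio | net ratio | net, simulated (20,000 trials) |
|---|---|---|---|
| 0.92 | 0.96 | 0.976 | 0.972 |
| 0.8 | 0.90 | 0.915 | 0.920 |
| 0.7 | 0.85 | 0.864 | 0.858 |
| 0.5 | 0.75 | 0.763 | 0.772 |

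Only 0.92 comes from the documents; the lower values are assumptions. The pilot had 2 weeks of therapy and a benefit "which sustained at follow-up (19 days post intervention"), against 6 weeks of therapy and a 1-month follow-up here, so a lower correlation is possible. Adjustment stops paying above rho = 2/(1 + 1/60) - 1 = 0.967, where it costs at most 1.7%.

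**3. Group effect averaged over the four times, rho = 0.92.** In units of s², unadjusted (1 + 3 rho)/4 + 1 - 2 rho = 0.10; adjusted (1 + 3 rho)/4 - rho² = 0.0936. The ratio is 0.936 (0.953 simulated, net of the slope).

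**4. Chance imbalance, rho = 0.92.** The SE of the baseline difference is 5.1 × sqrt(2/32) = 1.275 s. A 1-SE imbalance leaves 0.08 × 1.275 = 0.10 s in the estimate; a 1.96-SE imbalance leaves 0.20 s. The target is 4 s.

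**5. The group-by-time test.** Under compound symmetry, the last-minus-first post-baseline contrast is uncorrelated with baseline. Adding baseline with a baseline-by-time term gives a variance ratio of 1 + 1/60 = 1.017 (simulated 1.014 to 1.020), a slight loss. A common baseline slope leaves this test essentially unchanged.

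**6. Power at 10 weeks, 32 per group, under the two readings of 5.1 s and 0.92.**

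(a) *Raw times, baseline included.* Change SD = 5.1 × sqrt(2 × 0.08) = 2.04 s; adjusted SD = 5.1 × sqrt(1 - 0.92²) = 2.00 s. Power exceeds 99.9% either way. The single-time formula then gives n = 5.4, so about 6 per group rather than 32.

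(b) *SD and correlation of the analysed change.* This is the use that reproduces 32 in step 1. Power by the noncentral t, with R² the share of change variance explained by baseline (assumed):

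| analysis | power |
|---|---|
| unadjusted | 75.1% |
| adjusted, R² = 0 | 74.3% |
| adjusted, R² = 4% | 76.3% |
| adjusted, R² = 10% | 79.3% |
| adjusted, R² = 15% | 81.8% |
| adjusted, R² = 25% | 86.9% |

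With equal SDs, R² = (1 - r)/2, where r is the baseline-to-follow-up correlation, so 4% to 25% corresponds to r from 0.92 to 0.5. Power of 80% needs R² of about 11.4%.

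**The case against.** The strongest reply is that nothing is invalid and the documented loss is trivial. At 0.92 the SE of the 10-week difference falls only from 0.510 s to about 0.504 s (0.510 × sqrt(0.976)), and power exceeds 99.9% on the raw-time reading. That stands for that reading.

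It is also true that every larger gain rests on an assumed correlation or R², and that the match to 32 per group supports reading (b) without proving it.

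The comparison of 75% with 80% mixes two methods. The plan's 32 reproduces on the normal approximation, where the time-averaged test has 80.2% power and the 10-week contrast 77.4%. On the t scale these are 78.1% and 75.1%. The like-for-like gap is therefore about 3 points, and it comes from averaging over four times versus using one, not from omitting baseline. On the normal scale, without charging for the slope, adjustment gives 79.3%, 82.1%, 84.5% and 89.2% for the same four R² values. Either method puts unadjusted 10-week power below 80% under reading (b), and either shows adjustment raising it when baseline explains 4% or more.

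Finally, the plan reaches the 10-week comparison only after a significant group-by-time test, which adjustment does not help. The powers above ignore that step, so none is the power of the full procedure. This limits the practical benefit; it does not remove the gain in the estimate and its confidence interval.

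**Conclusion.** The concern holds as a point of precision, not validity. The model omits a covariate that is already collected and that usually improves the group effect and the 10-week difference.

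If 0.92 is the baseline-to-follow-up correlation and SDs are equal, the loss is small: 4% of variance at 10 weeks (2.4% net) and 6.4% for the time-averaged effect (4.7% net, simulated), with no practical effect on power. If that correlation is lower, the 10-week loss is 10% to 25% (8.5% to 23.8% net) over the assumed range 0.8 to 0.5. Under the reading that reproduces the sample size, this could decide whether 10-week power is below or above 80%. The documents do not settle which case applies, and give no correlation for the other outcomes. The worst outcome of adjusting is a variance penalty of at most 1.7%. The change is worth making, with moderate confidence about how much it will yield.

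**What to change.** Keep change from baseline as the outcome. In the Analysis paragraph of Section 10.0, add the participant's baseline value of the outcome concerned, and its interaction with time, as prespecified covariates in the repeated measures model for each outcome. State that the 10-week group difference is estimated from that model. The interaction lets the baseline slope differ by time; it is also the source of the 1.017 ratio for the group-by-time test.

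Separately, the sample size paragraph should say whether 5.1 s and 0.92 describe raw times or changes, since that determines how much the adjustment is likely to gain.

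The cost is a phrase of analysis wording and about one degree of freedom per time point. No new data are needed and the sample size does not change.

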1.0 Objectives / Specific Aims

The objective of this proposal is to determine if combining vibration with hand task practice is superior to hand task practice alone in an adequately powered study.

Aim 1: To determine clinical potential of vibration in improving hand functional recovery

Hypothesis: Improvement of hand motor function will be greater for the treatment than control.

Aim 2: To determine the effect of vibration on sensorimotor grip control and neural communication

Hypothesis: The treatment will enhance sensorimotor grip control via strengthened neural communication for hand grip, compared with control.

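### The 10-week comparison depends on a significant group-by-time interaction, which a benefit level across post-baseline visits cannot produce beyond chance

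*Combined protocol and SAP*

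**What the plan says.** The Analysis paragraph of section 10.0 fits a repeated measures ANOVA to each outcome. On the response it says: "The dependent variables will be the change from baseline at the evaluation times". On the model terms it says: "The primary independent variables are group, evaluation time, and their interaction"; sex and its interactions are added. The only decision rule is: "If the group by time interaction is significant, we will examine if there is a group difference at 10 weeks using post-hoc tests". Nothing states what is done when the interaction is not significant, at what level the interaction is tested, or what role the group main effect plays.

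The Sample size justification in the same section gives the target: "This study will be powered to detect difference at follow-up of at least 4s in movement time between the treatment and control groups". Its inputs are a "significance level of 0.017 (adjusted for multiple comparison") and "at least 80% power, and 4 time points, for a standard deviation (SD) of 5.1s and compound symmetry correlation of 0.92", leading to 32 evaluable per group and 38 per group after 15% attrition.

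Section 9.0 (Study design) sets the visits: "Evaluation will be performed at baseline, after 2, 4, and 6 weeks of continuous task practices and at 1-month follow-up". The Schedule paragraph that follows lists only baseline, end of therapy and follow-up. The Aim 1 hypothesis in section 1.0 names no time point: "Improvement of hand motor function will be greater for the treatment than control".

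**The concern.** With change from baseline as the response, every level of the time factor is a post-baseline visit. The group-by-time interaction then tests whether the treatment difference changes between those visits. It does not test whether there is a difference. A treatment that gives the same benefit at weeks 2, 4, 6 and 10 has a zero interaction, however large the benefit.

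As the rule stands, access to the 10-week comparison depends on how the benefit varies between earlier visits and not on its size at 10 weeks. The trial could show a sustained benefit and still have no pre-specified way to test the difference it says it was sized to detect. Moving to another test after seeing a null interaction would be an unwritten decision about the primary analysis.

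**Working it through.** **Inputs.** From section 10.0: 32 evaluable per group, SD 5.1 s, compound-symmetry correlation 0.92, difference 4 s, alpha 0.017, power 80%, 4 time points. Assumed: two-sided tests, sex terms omitted, and a true 10-week benefit of 4 s in every scenario. The benefit at the other visits is assumed because the documents do not give it. The gate's alpha is not stated, so results are shown at 0.017 / 0.05.

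**1. The plan's own sample size.** Normal approximation: n = 2(z₀.₀₀₈₅ + z₀.₂₀)² V / 4².
- Average over four visits: V = 5.1² × (1 + 3 × 0.92)/4 = 26.01 × 0.94 = 24.45, so n = 31.9. This gives the stated 32; 32/0.85 = 37.6, which gives the stated 38.
- Single visit: V = 5.1² = 26.01, so n = 33.9.

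The stated figure therefore matches a level 4 s difference averaged over four visits, which is the pattern the gate cannot see. The plan does not state its formula, so this is a match and not proof.

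**2. Chance that the gate opens.** Noncentral F with T visits, degrees of freedom T−1 and 62(T−1), and

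ncp = (32/2) × Σ(d_t − mean d)² / (5.1² × 0.08), with denominator 2.081.

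| Benefit by visit (s) | Σ(d_t − mean d)² | ncp | Gate opens, 0.017 / 0.05 |
|---|---|---|---|
| 4, 4, 4, 4 | 0 | 0 | 1.7% / 5% |
| 3.5, 4, 4, 4 | 0.1875 | 1.44 | 7% / 15% |
| 3, 4, 4, 4 | 0.75 | 5.77 | 33% / 49% |
| 2, 3, 4, 4 | 2.75 | 21.1 | 95% / 98% |
| 2, 4, 4, 4 | 3.00 | 23.1 | 96% / 99% |
| Weeks 6 and 10 only: 4, 4 | 0 | 0 | 1.7% / 5% |
| Weeks 6 and 10 only: 3, 4 | 0.50 | 3.84 | 32% / 49% |

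The level rows do not depend on n, SD or correlation. The table also does not depend on whether 5.1 s is the SD of change scores or of raw scores. On the raw-score reading the change SD is 5.1 × √(2 × 0.08) = 2.04 and changes correlate 0.5, so the residual variance is 2.04² × 0.5 = 2.08, as before.

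**3. Tests without the gate.**
- Direct 10-week test: ncp = 16 × 4²/26.01 = 9.84 on 1 and 62 df. Power is 75% / 87% on the change-score reading and over 99% on the raw-score reading.
- Group main effect, level 4 s: ncp = 16 × 4²/24.45 = 10.47 on 1 and 62 df. Power is 78% / 89% on the change-score reading and over 99% on the raw-score reading.

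**4. Rules in sequence** (simulation, 40,000 replicates, change-score reading, both tests at the same alpha).

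| Benefit (s) | Gate opens and week 10 significant | Week 10 if gate opens, otherwise main effect |
|---|---|---|
| 4, 4, 4, 4 | 1.3% / 4.3% | 78% / 89% |
| 3.5, 4, 4, 4 | 5% / 13% | 75% / 87% |
| 3, 4, 4, 4 | 25% / 43% | 74% / 86% |
| 2, 3, 4, 4 | 71% / 86% | 74% / 87% |

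The last column is a sequence the plan does not contain. With weeks 6 and 10 only and 3, 4 s, that sequence gives 69% / 85%.

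**The case against.** The strongest reply has four parts.

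- **The text says if, not only if.** Group is a primary model term, and reading the main effect when the interaction is absent is ordinary practice. It would answer Aim 1, and 32 per group fits that test. With such a fallback, detection of some group effect is close to that of a direct test. All of this is true. But the fallback is not written, and the main effect estimates a visit average. In the exactly level case the two quantities are the same 4 s; in every other case they differ, and the plan names the follow-up difference as its target.
- **The 98% belongs to one time course.** It requires the full benefit by week 2 of a 6-week therapy. A benefit proportional to therapy received and then held (1.3, 2.7, 4, 4 s) opens the gate in 99.9% of trials at alpha 0.017. That stands. It also shows the weakness: the rule works only if the benefit moves between visits. It relies on the high correlation too; at an assumed 0.6, even 2, 3, 4, 4 s opens the gate in only 22% (37% at 0.05).
- **Power is not literally zero.** Correct: under a level benefit it equals the gate's alpha.
- **Choosing 10 weeks is a choice of estimand, and costs a little power in the level case** (75% against 78% at alpha 0.017). The cost is real, but the choice follows the plan's own powering statement.

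**Conclusion.** The concern holds and needs correcting. The written rule makes the follow-up comparison conditional on a test that has no power beyond its alpha when the benefit is level across post-baseline visits. In that case the comparison is withheld in about 98% of trials at alpha 0.017, or 95% at 0.05. For a modest early shortfall (3, 4, 4, 4 s) it is withheld in about 67% or 51%. For a clearly building benefit the gate does little harm at the plan's correlation.

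The loss applies to the 10-week claim and not to every possible group test. The result rests on baseline not being a level of time, which the change-from-baseline response establishes, and on the absence of any other stated route. The near-level figures also rest on the assumed time courses, compound symmetry at 0.92 and omission of the sex terms. The level result needs none of the numerical inputs except the gate's alpha.

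**What to change.** In the Analysis paragraph of section 10.0, delete the interaction condition. State instead that the primary test is the between-group contrast at the 1-month follow-up (10 weeks), estimated from the same repeated-measures model with group-by-time included, whatever the interaction p-value, and give its alpha. Report the interaction, the group main effect and the other visits as secondary.

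The change is one sentence and needs no new data. The sample-size paragraph should also say whether 5.1 s is a change-score or raw-score SD. If it is a change-score SD, power for this contrast at 32 per group and alpha 0.017 should be restated as about 75%. Reaching 80% takes about 36 evaluable per group (35 gives 79.5%, 36 gives 80.9%), which after 15% attrition is 36/0.85 = 42.4, or 43 per group and 86 in total against the planned 76. Raising enrolment is optional; restating the power is not. If it is a raw-score SD, power exceeds 99% and nothing is lost.

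### The stated 80% power for a 4 s difference at follow-up belongs to a four-visit average, and the follow-up test itself is run only if the group-by-time interaction is significant

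*Combined protocol and SAP*

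**What the plan says.** Section 10.0 (Data Management) holds both the analysis and the sample size.

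- **Target.** "This study will be powered to detect difference at follow-up of at least 4s in movement time between the treatment and control groups".
- **Inputs.** A "significance level of 0.017 (adjusted for multiple comparison"), at least 80% power, four time points, and "for a standard deviation (SD) of 5.1s and compound symmetry correlation of 0.92", both taken from the pilot study. The result is 32 per group, raised to 38 per group (76 in total) for 15% attrition.
- **Model.** Every outcome is analysed by repeated measures ANOVA. On what is analysed, the plan says: "The dependent variables will be the change from baseline at the evaluation times". On the factors in the model, it says: "The primary independent variables are group, evaluation time, and their interaction". Sex is added with its interactions.
- **Follow-up test.** "If the group by time interaction is significant, we will examine if there is a group difference at 10 weeks using post-hoc tests".

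No power is given for the interaction, and no pattern of group differences over time is assumed.

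Section 9.0 describes the evaluations in two ways. The study design paragraph says: "Evaluation will be performed at baseline, after 2, 4, and 6 weeks of continuous task practices and at 1-month follow-up". The schedule paragraph counts evaluation visits "for each of the 3 time points (baseline, after therapy, and follow-up").

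**The concern.** Three things should refer to the same quantity, and they do not. The stated target is the group difference at one visit. The calculation appears to be for a difference averaged over four visits, which in this model is the group main effect. The test of the target is conditional on a third quantity, the interaction.

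The conditional step matters most. Baseline is subtracted from every outcome, so it is not a level of the time factor. The interaction therefore asks only whether the benefit differs among the post-baseline visits. A benefit that appears early and holds sits almost entirely in the group main effect, and under the written rule the 10-week comparison would then usually not be made. The sponsor's background (section 2.0) makes such a pattern plausible: one pilot found an advantage after two weeks of therapy that was still present at follow-up. That pilot's outcome was the Box and Block Test, not movement time, so it shows plausibility only.

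Readers will use the power sentence to interpret a null or missing 10-week result, and as written it does not describe that result.

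**Working it through.** **Inputs (section 10.0).** Difference 4 s, SD 5.1 s, correlation 0.92 (compound symmetry), alpha 0.017, power 80%, 4 time points, 15% attrition. Two-sided alpha is assumed because it reproduces the stated n. The formula is inferred, since the plan names none.

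**1. Reproducing the plan's figure.**
- z(0.9915) + z(0.80) = 2.387 + 0.842 = 3.228.
- Single visit: n = 2 × 3.228² × (5.1/4)² = 33.88, so 34 per group.
- Mean of m visits: multiply by (1 + (m−1) × 0.92)/m. For m=4 the factor is 3.76/4 = 0.94, and 33.88 × 0.94 = 31.85, so **32 per group**.
- Attrition: 32/0.85 = 37.6, so 38 per group and 76 in total.

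The stated figures are reproduced. By the same formula m=2 and m=3 give 33 (32.53 and 32.08), and m=5 to 9 also give 32. The stated four time points fit but are not the only fit.

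**2. Power for the stated target, ignoring the gate** (32 per group, two-sided 0.017).

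| Reading of 5.1 s | SD of change | Power for 4 s at follow-up | Difference with 80% power (t) |
|---|---|---|---|
| SD of change | 5.1 s | 75% (t), 77% (normal) | about 4.2 s |
| SD of raw times | 5.1 × √(2 × 0.08) = 2.04 s | over 99.9% | about 1.7 s |

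On the change-SD reading, 80% power by t needs 36 per group. If all 38 per group complete, power is 83%. One-sided 0.017 at 32 per group also gives 83%. The four-visit mean at 32 per group has 80.2% power (normal) or 78% (t).

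**3. The gate.** With 4 visits and 32 per group, the interaction is tested on F(3, 186), with critical value 3.48 at 0.017. The error variance is 5.1² × (1 − 0.92) = 2.08. This is the same on both readings in step 2, because the baseline value subtracted is common to all visits. The non-centrality is (32/2) × Σ(d − d̄)²/2.08, where d is the group difference at each visit. The patterns are illustrative, since the plan gives none, and sex terms are ignored.

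| Benefit at weeks 2, 4, 6, 10 (s) | Σ(d − d̄)² | Non-centrality | Passes at 0.017 | Passes at 0.05 |
|---|---|---|---|---|
| 4, 4, 4, 4 | 0 | 0 | 1.7% | 5% |
| 3, 4, 4, 4 | 0.75 | 5.77 | 32% | 49% |
| 1, 2, 3, 4 | 5 | 38.4 | 99.9% | over 99.9% |

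**4. Passing the gate and then the 10-week test, both at 0.017** (simulation, 40,000 runs).

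| Pattern (s) | Change-SD reading | Raw-SD reading |
|---|---|---|
| 4, 4, 4, 4 | about 1% | about 2% |
| 3, 4, 4, 4 | 25% | 32% |
| 1, 2, 3, 4 | 75% | 99.9% |

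**5. The reverse case.** For the 1, 2, 3, 4 s ramp the averaged difference is only 10/4 = 2.5 s. On the change-SD reading the group main effect then has 34% power (t). The calculation that gave 32 per group therefore equals a 4 s difference at follow-up only when the benefit is constant, which is the pattern the gate blocks.

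**6. Number of evaluations.** The study design paragraph in section 9.0 gives four post-baseline evaluations, matching the four time points in the calculation. The schedule paragraph's count is 18 therapy visits + 2 × 3 evaluation visits + 1 MRI = 25, which covers only two post-baseline evaluations. It does not say where the week 2 and week 4 evaluations take place. With m=2 the formula gives 33 per group.

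**The case against.** **The arithmetic is right and the averaging costs little.** This stands. At a correlation of 0.92, averaging changes n only from 34 to 32. About 3 points of power are due to averaging (78% against 75%, both by t); the rest of the shortfall from 80% comes from using t instead of the normal distribution. On the raw-SD reading the plan is conservative.

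**The group effect is tested whatever the interaction shows.** This also stands, and it limits the consequence. With a constant benefit the main effect equals the 4 s follow-up difference. Counting success by either route (main effect, or interaction followed by the 10-week test), the change-SD reading gives about 78%, 74% and 75% for the three patterns, close to the 75% of an ungated 10-week test. But success by either route is not one test with controlled alpha, and the plan names the follow-up difference as its target. A significant main effect opens no 10-week test under the written rule.

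**The SD and correlation may describe different variables.** If 5.1 s were the SD of change and 0.92 the correlation of raw times, the gate's error variance would be 5.1²/(2 × 0.08) × 0.08 = 13.0. Then 3, 4, 4, 4 s would pass about 5% of the time and 1, 2, 3, 4 s about 35%. The plan's own calculation appears to apply both figures to one variable, so this reading is less likely. It would make the gate harder to pass and leaves the constant-benefit result unchanged.

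**The week 2 and week 4 evaluations could take place within therapy visits.** Possibly, since section 9.0 allows therapy visits up to 2.5 hours. The plan does not say so, and the effect on n is one participant per group.

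**Conclusion.** The concern holds. The plan claims at least 80% power for a difference at follow-up, its sample size fits a four-visit average, and its rule tests the follow-up difference only after a significant interaction. The gate is the serious part: a constant 4 s benefit would reach the 10-week test at only the alpha rate, and this holds for any SD or correlation. The averaging mismatch is minor.

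The 1.7% assumes that the interaction is tested at 0.017; the plan does not state its alpha. The pass rates for the other patterns also rest on 5.1 s and 0.92 describing the same variable and on the patterns chosen here. The follow-up power of 75% or over 99.9% depends on which variable the SD describes, and on a two-sided alpha.

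This is a mismatch to correct and not evidence that 76 participants are too few.

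**What to change.** Keep n=76 and change the text as follows.

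1. In the analysis paragraph of section 10.0, make the group difference in change from baseline at 10 weeks a pre-specified contrast from the repeated measures model, tested at 0.017 whatever the interaction shows. Report the interaction and the group main effect as supporting results.
2. State whether 5.1 s and 0.92 describe raw times or change scores, whether 0.017 is two-sided, and which comparisons it adjusts for.
3. Replace the claim of at least 80% power for 4 s with the t-based figures for that contrast at 32 evaluable per group: 75% for 4 s (80% for about 4.2 s) if 5.1 s is the SD of change, or over 99.9% (80% for about 1.7 s) if it is the SD of raw times.
4. In section 9.0, say when the week 2 and week 4 evaluations take place and which outcomes they include, or correct the number of time points in the calculation.

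The cost is rewriting two paragraphs and one schedule sentence, with no added participants. The contrast uses the alpha that the sample size paragraph already attaches to the follow-up difference, so removing the gate adds no further test. On the change-SD reading the sponsor would have to state 75% power in place of at least 80%.
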